10.4. Vital Signs

Subject minimum and maximum post-baseline systolic and diastolic blood pressures, respiratory rate, pulse rate, temperature and body weight (and changes from baseline) will be summarized by the mean, standard deviation, median, minimum and maximum values. The same statistics will be calculated to summarize vital signs by visit.

10.5. Electrocardiograms

ECG QTc measurements will be summarized with descriptive statistics and time point with respect to BIO 300 Oral Powder administration. All ECG data will be displayed in a data listing.

11. Symbols and Abbreviations

AE	Adverse Event
ANOVA	Analysis of Variance
AUC	Area Under the Curve
BAM	Binary Alignment Map
BLQ	Below the Limit of Quantitation
BMI	Body-Mass Index
CBC	Complete Blood Count
Cmax	Maximum (Peak) Serum Concentration
DLT	Dose Limiting Toxicity
ECG	Electrocardiogram
F	Female
FDA	U.S. Food and Drug Administration
ITT	Intent to Treat
Inf	Infinity
M	Male
Max	Maximum
Min	Minimum
mL	Milliliter
MSD	Multiple Single Dose
ng	Nanogram
PCA	Principal component analysis
PD	Pharmacodynamics
PK	Pharmacokinetics
QTc	Corrected QT Interval
RNA	Ribonucleic Acid
SAD	Single Ascending Dose
SAE	Serios Adverse Event
SAP	Statistical Analysis Plan
SMC	Safety Monitoring Committee
SOC	System Organ Classification
STD	Standard Deviation
t	time
T1/2	Half-Life
Tmax	Time to Reach Maximum (Peak) Serum Concentration

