8.2 SAFETY AND OTHER ASSESSMENTS

Physical Exam – Examination of the participant’s cardiovascular, HEENT, lymphatic, pulmonary, gastrointestinal, musculoskeletal, and neurological systems.

Vital Signs – Vital signs will record the patient’s height, weight and BMI. They will also measure heart rate, blood pressure (systolic and diastolic), respiratory rate, and body temperature.

Electrocardiogram – ECGs occur during the screening visit, on visit 2 (1 hr before, 1hr after, 2 hrs after and 4 hrs after BIO 300 Oral Powder dose), and visits 3-5 for the SAD phase. ECGs will occur during the screening visit, visit 2 (1 hr before, 1hr after, 2 hrs after and 4 hrs after BIO 300 Oral Powder dose), visits 3-4, visit 7 and visit 10 for the multiple single dose phase. ECGs will be digitally read locally at the study site. ECGs will be completed in triplicate and the average will be used to determine if the study subject has an abnormal reading.

QTc Interval Prolongation – Fridericia-corrected QTc (QTcF) interval from all subjects in both the SAD and the multiple single dose studies will be used to evaluate QTcF interval prolongation. QTcF prolongation will be determined by evaluating ECG at baseline (pre-dose) and at multiple time points around the predicted C_{max} of BIO 300 Oral Powder (ECG timepoints listed above). QTcF intervals will be reported for each dosing cohort as a mean and standard deviation. The upper limit for QTcF interval prolongation will be >480 ms or absolute QTcF change from baseline of >30 ms with a 95% confidence interval. The relationship between drug exposure and mean QTcF interval change will be evaluated in the SAD study using both C_{max} and AUC. Any adverse events that may signal a potential proarrhythmic effect will be carefully monitored (e.g., Torsade de pointes, sudden death, ventricular tachycardia, seizures, etc.).

Complete Blood Count – Blood sampling for the laboratory parameters will be performed during the screening and BIO 300 Oral Powder treatment period according to the study schedule (**Section 1.3**). A complete blood count with differential will evaluate hemoglobin, hematocrit, red blood cells (RBCs), white blood cells (WBCs), neutrophils, lymphocytes, monocytes, eosinophils, basophils, and platelet count.

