7.1. Definitions

- Baseline is synonymous with screening, and the baseline value (or baseline result) is that measured during the screening visit prior to the first administration of BIO 300 Oral Powder.
- Day 1 is the first day of dosing with BIO 300 Oral Powder.
- Estimand is the estimated value for a parameter or, alternatively, a formula and/or description for how a parameter is estimated.
- Proportional months, defined for durations of time reported in months, are given by the formula

$$\text{months} = \frac{12}{365.25} \times \text{days}$$

- Shift table is a two-way frequency table pairing baseline value with the most extreme post-baseline result.

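### The SAP does not carry over the protocol's QTcF evaluation (correction, pre-dose baseline, limits, exposure relation), and the 30 ms confidence-interval criterion cannot be applied as written

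*Combined protocol and SAP*

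**What the plan says.** Protocol 8.2, under ECG and QTc interval prolongation, sets out a specific evaluation for both parts of the study. ECGs are taken in triplicate and averaged, the interval is Fridericia-corrected, and baseline is the pre-dose ECG. "QTcF intervals will be reported for each dosing cohort as a mean and standard deviation". The upper limit for prolongation is ">480 ms or absolute QTcF change from baseline of >30 ms with a 95% confidence interval". Then: "The relationship between drug exposure and mean QTcF interval change will be evaluated in the SAD study using both" Cmax and AUC.

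SAP 10.5 says that "ECG QTc measurements will be summarized with descriptive statistics and time point with respect to BIO 300 Oral Powder administration", and that all ECG data are listed. SAP section 7 adds two general rules: change from baseline is computed for every measured variable, and dose groups are compared on it by ANCOVA with baseline as covariate. Its definition of descriptive statistics includes the maximum and standard errors or confidence intervals. SAP 7.1 states that "Baseline is synonymous with screening".

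**The concern.** ECG is named among the safety assessments in the primary endpoint (Protocol section 3). A statistician working from the SAP would produce QTc summaries with no stated correction, changes measured from a screening ECG, no count of subjects over either protocol limit, and no exposure-QTcF analysis. The SAP says that it leaves out only protocol matter unrelated to statistics, so silence here is hard to read as incorporation by reference.

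The protocol text has its own gap. Attaching a confidence interval to a 30 ms change does not say whether the change is one subject's or a cohort mean, which bound must cross 30 ms, or at which time point. Two analysts could look at the same cohort and reach opposite answers on whether the limit was exceeded.

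**Working it through.** **1. The two documents side by side**

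| Item | Protocol | SAP |
|---|---|---|
| Correction | Fridericia (8.2) | QTc, method not named (10.5) |
| Triplicate | average used (8.2) | not mentioned |
| Baseline | pre-dose ECG for QTcF (8.2); screening in general (9.1) | screening (7.1), which the schedule places at Day -28 to -8 |
| Limits | 480 ms; 30 ms change (8.2) | no count or flag |
| Change and dose comparison | cohort mean and SD (8.2); ANCOVA (9.4.2) | generic change from baseline and ANCOVA (7) |
| Exposure relation | Cmax and AUC, SAD (8.2) | none in 9.2 or 10.5 |

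The baseline conflict therefore also runs inside the protocol, between 8.2 and 9.1.

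**2. What the 30 ms criterion means under each reading**

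The documents give no precision or power figure for QTc, so there is none to reproduce. Inputs: n = 6 per SAD cohort and 8 in the multiple single dose (MSD) cohort (Protocol 9.2). The SD of QTcF change is not in the documents, so 8 to 20 ms is assumed.

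Half-width h = t(0.975, n-1) × SD / √n. For n = 6, t = 2.571. At SD 10, h = 2.571 × 10 / √6 = 10.5 ms.

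| Assumed SD (ms) | h, n = 6 (ms) | Met above, if upper bound must exceed 30 | Met above, if lower bound must exceed 30 |
|---|---|---|---|
| 8 | 8.4 | 21.6 | 38.4 |
| 10 | 10.5 | 19.5 | 40.5 |
| 15 | 15.7 | 14.3 | 45.7 |
| 20 | 21.0 | 9.0 | 51.0 |

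The last two columns are observed cohort mean changes, 30 - h and 30 + h. They differ by 2h, or 16.8 to 42.0 ms over this range. For n = 8 (t = 2.365), h is 6.7, 8.4, 12.5 and 16.7 ms. If the limit is meant for one subject's change, the documents define no interval for it.

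**3. The Cmax/AUC evaluation**

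Protocol 8.2 names no model, and the mean change could be a cohort mean or each subject's triplicate average. The correlation needed for two-sided p < 0.05 is t / √(df + t²):

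- 4 cohort means, 2 df: r above 0.950 (R² 0.90)
- 24 subjects (4 × 6), 22 df: r above 0.404 (R² 0.16)

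Power for a linear slope, assuming exposures in ratio 1:2:4:8 and SD 10 ms (SD 8 to 15 ms in brackets):

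| True effect at top exposure | 4 means | 24 subjects |
|---|---|---|
| 10 ms | 17% (10 to 23%) | 35% (18 to 50%) |
| 20 ms | 44% (25 to 58%) | 88% (55 to 97%) |

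**4. Which ECGs are matched to a concentration**

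On Day 1 of both parts, ECG and PK are both scheduled at 1, 2 and 4 h. That gives 24 × 3 = 72 SAD pairs and 8 × 3 = 24 MSD pairs. The pairs are correlated within subject, so the independent units remain 24 and 8. ECGs on SAD Days 2 and 3 and on MSD Day 6 have no clock time in the schedule.

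After a SAD dose no ECG is scheduled between 4 h and Day 2. The amendment history says that the MSD Day 6 biomarker draws were reset using the Cmax seen in all four SAD cohorts, and the schedule now puts the post-dose draws that day at 4, 8 and 12 h. No Tmax is given.

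**The case against.** The best defence is that SAP 10.5 should not be read alone. Section 7 already gives QTc a change from baseline, confidence intervals and an ANCOVA across doses, and Protocol 9.4.2 plans baseline-adjusted ANCOVA for ECGs. With 6 subjects per cohort, a value over 480 ms would show in the maximum and in the listing. All of that stands. It does not supply the correction, the pre-dose baseline, the counts or the exposure relation.

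Four stronger readings are tempting, and the documents do not support them.

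- *The SAP offers only descriptive QTc.* True of 10.5 alone; section 7 goes further.
- *The protocol's limits are unusable.* The 480 ms limit works as written on individual values. Only the interval criterion fails.
- *The Cmax/AUC evaluation throws away most of the data.* Counting 72 pairs against 24 points overstates the gain, because the pairs are repeated measures on the same 24 subjects. At subject level the evaluation has fair power for a large effect and little for a small one.
- *The 1 to 4 h ECGs missed the peak and flatten the slope.* The reset Day 6 draws make a later peak possible, but without a Tmax, and with 4 h itself an ECG time, this is not established or quantified.

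One might also suspect a version effect, since the SAP cites protocol version 1.0 and the protocol supplied runs to 2.0. The amendment history lists no ECG change, though version 1.0 is not available to confirm its text.

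**Conclusion.** The concern holds in a limited form. Followed as written, the SAP does not deliver the QTcF evaluation that Protocol 8.2 describes, and its screening baseline contradicts the pre-dose baseline given there. The 30 ms interval criterion is undefined. At n = 6 and an assumed SD of 10 ms, the choice of bound moves the threshold on the cohort mean from 19.5 to 40.5 ms. The size depends on the assumed SD, but the ambiguity exists at any SD. The Cmax/AUC evaluation needs restoring and specifying at subject level; it does not need replacing. This should be corrected, but it is not a failure of the trial's safety monitoring.

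**What to change.** Rewrite SAP 10.5 as follows.

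1. Analyse QTcF as the triplicate mean, with change from the Day 1 pre-dose ECG. Reconcile this with the screening baseline in SAP 7.1 and Protocol 9.1.
2. Count subjects over each existing protocol limit at any post-dose time, as individual flags.
3. Separately, report mean QTcF change with its two-sided 95% confidence interval by time point and cohort, and reconcile the wording of Protocol 8.2 so that the interval belongs to the mean and not to the flag.
4. Restore the Cmax and AUC evaluation in the SAD at subject level. Beside it, add a linear mixed model of QTcF change on genistein concentration at the matched 1, 2 and 4 h times, with a random subject effect, labelled exploratory. Use SAD Day 1. If MSD is pooled, use MSD Day 1 only, unless actual ECG times on other days are recorded.
5. State as a limitation that no ECG is scheduled between 4 h and Day 2 after a SAD dose, so a later peak is unobserved and the model cannot recover it.

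The cost is a little more programming and the wording changes. No new visit, ECG or blood sample is needed. If SAD ECG data have been seen by the time this is written, the SAP should say so.
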